# 5.4.6 Maximum Tolerated Dose

# 5.4.6.1 MTD Definition

The MTD will be defined as follows in each of the Phase 1 parts:

- KY1044 single agent: the MTD is defined as the highest drug dosage not expected to cause DLT in 30% or more of the treated patients in the DLT follow-up period, corresponding to the first 21 days of KY1044 treatment during the escalation part of the study.
- KY1044 combination with atezolizumab: the MTD is defined as the highest drug dosage not expected to cause DLT in 30% or more of the treated patients in the DLT follow-up period, corresponding to the first 21 days of combined treatment during the escalation part of the study.
- The SRC will use all data previously mentioned as well as the mTPI-2 decision table in determining the MTD. The MTD is determined based on the isotonic regression specified in Guo et al. 2017 (49). The determined MTD is the dose for which the isotonic estimate of the toxicity rate is the closest to the target toxicity rate of 30% and

less than 35%. The parameters of mTPI-2 design and operating characteristics are described in Section 9.

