# 9 STATISTICAL CONSIDERATIONS

# 9.1 Modified Toxicity Probability Interval (mTPI-2) Design

### 9.1.1 Rationale for mTPI-2 Design

The rationale for deciding the starting dose and investigational dose range are discussed in the previous Section 5.4.1. In the trial, dose escalation/de-escalation decisions will use predefined DLT criteria (Section 5.5) and be based on the mTPI-2 design (49) with precalculated decisions that are displayed in Figure 9-1 (obtained via U-Design v1.0, udesign.laiyaconsulting.com). Figure 9-1 consists of all the dose-escalation rules for the trial. The trial is conducted aiming at a target 30% DLT rate ( $p_T=30\%$ ) for the MTD with an acceptable DLT range of 25% to 35%, and a maximum sample size of 36 patients with a cohort size of 3. To begin the trial, treat three patients on the starting dose. After observing all the outcomes of each cohort (or as specified in Section 5.4.3 if cohort modification is required), dose-escalation, de-escalation or staying at the current dose will be guided by the decision table and the SRC.

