### Figure 9-1: mTPI-2 Decision Table

Sample size=36, Target toxicity probability=0.3, epsilon 1=0.05, epsilon 2=0.05

\* Column indicates the number of patients treated. Row indicates the number of patients with DLTs

\*  $\mathbf{E}$ : Escalate to the next higher dose;  $\mathbf{S}$ : Stay at the same dose;  $\mathbf{D}$ : De-escalate to the previous lower dose;  $\mathbf{D}$ : De-escalate to the previous lower dose and the current dose will never be used again in the trial. Two parameters e1 and e2 are set at default values (Guo. et al. 2017) of 0.05.

The mTPI-2 design is chosen for this trial because it has demonstrated superior operating characteristics when compared with standard methods, such as the 3+3 design, and is easy to implement with precalculated dose decision rules (56).

Section 9.1.2 presents comprehensive simulation results of mTPI-2 and its operating characteristics. See Appendix 4 for the detailed technical summary of the design and simulations.

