#### 9.1.2 Simulation Results

Simulations were performed via U-Design v1.0 to assess the performance of mTPI-2 based on the setting of this trial. There are seven prespecified doses and the stating dose is 0.8 mg. The sample size is 36 and patients are enrolled in cohorts of size 3. The MTD target toxicity probability is  $p_T=0.3$  and the choices of  $e_1$  and  $e_2$  are both 0.05. Six different scenarios were investigated in the simulation studies, as shown in Table 9-1 and Figure 9-1. For each scenario, 5000 simulated trials were conducted.

Index		naim	Dose (mg)						
	p T	nsim	0.24	0.8*	2.4	8	24	80	240
1	0.3	5000	0.001	0.005	0.022	0.0831	0.269	0.599	0.858
2	0.3	5000	0.668	0.832	0.924	0.968	0.987	0.995	0.998
3	0.3	5000	0.002	0.008	0.039	0.168	0.500	0.832	0.961
4	0.3	5000	0.001	0.018	0.269	0.881	0.993	0.9997	0.99998
5	0.3	5000	0.063	0.083	0.109	0.142	0.182	0.231	0.289
6	0.3	5000	0.039	0.083	0.168	0.310	0.500	0.690	0.832

 Table 9-1:
 Six Scenarios Used in Simulation Results

\*starting dose

The simulation results are presented in Figure 9-2 and Table 9-2.

Figure 9-2 illustrates the performance of mTPI-2 in terms of the probability of selecting the MTD, probability of toxicity, probability of selecting a dose higher than the MTD, and the probability of no selection.

Table 9-2 provides a summary of these results. The full details of each of the six simulations is presented in Appendix 4.

Figure 9-2:	mTPI-2 Performance	Across	the Six	Scenarios
-------------	--------------------	--------	---------	-----------

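### Section 5.4.6.1 gives two MTD rules that conflict for DLT estimates from 30% to under 35%, and Table 9-2's 0.712 counts a scenario with no MTD as a correct selection (0.654 without it)

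*Protocol*

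**What the plan says.** Protocol Section 5.4.6.1 defines the MTD in its first two bullets, once for single agent and once for the combination, in the same terms: "the MTD is defined as the highest drug dosage not expected to cause DLT in 30% or more of the treated patients" over the first 21 days.

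The third bullet then bases the determination on isotonic regression. It takes the "dose for which the isotonic estimate of the toxicity rate is the closest to the target toxicity rate of 30" percent, on the added condition that the estimate is below 35%.

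Section 9.1.1 sets a 30% target "for the MTD with an acceptable DLT range of 25% to 35" percent, which agrees with the third bullet. The design settings under Figure 9-1 are "Sample size=36, Target toxicity probability=0.3, epsilon 1=0.05, epsilon 2=0.05".

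Table 9-2 reports a probability of selecting the MTD of 0.712±0.223, with scenario detail in Appendix 4. The SAP's study design section (6.0) points to the mTPI-2 decision table and gives no rule for estimating the MTD.

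**The concern.** A dose estimated at 30% or more but under 35% fails the first two bullets and can be the MTD under the third. No sentence ranks the two. With cohorts of three this zone is easily reached, because 1/3, 2/6, 3/9 and 4/12 all equal 33.3%.

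Identifying recommended doses is part of the Phase 1 primary objective, and other provisions depend on the MTD:

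- Section 5.4.4 requires that the combination starting dose not exceed the single-agent MTD.
- The footnotes to Tables 5-2 and 5-3 allow extra cohorts below the MTD.
- Section 3.1.4 opens the Phase 2 dose assessment when no MTD or single efficacious dose has been found.

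The same DLT data could therefore give the SRC two different MTDs, with operating characteristics published for only one of the rules.

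A separate matter is Appendix 4, Scenario 2. Every true DLT rate there is at least 0.668 and no dose is ever selected. The scenario is nevertheless scored 1 for selecting the MTD and also 1 for no selection. Averaging that 1 into Table 9-2 would overstate how often the design finds an MTD that exists.

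**Working it through.** **1. Reproduce Table 9-2.** The inputs are the six scenario values in Appendix 4.

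- Selecting the MTD: (0.73 + 1 + 0.876 + 0.749 + 0.398 + 0.516)/6 = 4.269/6 = 0.7115, sample SD 0.223. This matches 0.712±0.223.
- Selecting above the MTD: (0.026 + 0 + 0.091 + 0.001 + 0 + 0.069)/6 = 0.187/6 = 0.031. This matches.
- No selection: 1/6 = 0.167, SD 0.408. This matches, and the 1 is again Scenario 2.

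**2. Remove Scenario 2 from the first row.** (0.73 + 0.876 + 0.749 + 0.398 + 0.516)/5 = 3.269/5 = 0.654, SD 0.193.

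**3. Where the rules part.** Take a dose estimated at 33.3%. Its distance from 30% is 3.3 points and it is below 35%, so the third bullet selects it unless a lower dose is estimated nearer to 30%, that is above 26.7%. The first two bullets exclude it. Recomputing the mTPI-2 decisions gives Stay for 1/3, 2/6, 3/9 and 4/12, so the design tends to keep treating at such a dose.

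**4. How often the rules differ.** The design was re-simulated with 10,000 trials per scenario, using the protocol's seven doses, start at 0.8 mg, cohorts of 3, 36 patients, target 0.30 and both epsilons 0.05. Assumptions not stated in the protocol:

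- a Beta(1,1) prior for the dose decisions;
- exclusion of a dose when the probability that its rate exceeds 0.30 is above 0.95;
- isotonic regression over the doses tried.

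The under-35% rule takes the estimate nearest 0.30 and below 0.35. The under-30% rule takes the highest non-excluded dose with an estimate below 0.30.

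| Scenario | MTD selected, Appendix 4 | Re-simulated, under-35% rule | Trials in which the rules differ |
|---|---|---|---|
| 1 | 0.73 | 0.724 | 12.1% |
| 2 | 1 (no dose selected) | no dose selected | 0% |
| 3 | 0.876 | 0.876 | 7.5% |
| 4 | 0.749 | 0.754 | 14.0% |
| 5 | 0.398 | 0.395 | 22.3% |
| 6 | 0.516 | 0.521 | 17.0% |

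The Monte Carlo standard error of the last column is at most √(0.223 × 0.777/10,000) = 0.4 points. A second simulation of the same size gave 12.6%, 6.9%, 13.9%, 21.9% and 16.2% for Scenarios 1, 3, 4, 5 and 6. In every discordant trial the under-35% rule named the higher dose, with an estimate between 30% and 35%. Weighting the isotonic fit by sample size or by variance made no difference.

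**5. Which rule the published figures follow.** With the 35% cap removed, Scenario 3 would give 0.753 and Scenario 4 would give 0.889, against the published 0.876 and 0.749. The published figures therefore use the cap. Scenario 6 shows the same thing directly, since it scores the dose with true rate 0.310 as the MTD.

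**6. Under-30% rule for both selection and scoring.** The MTD is now the highest dose with a true rate below 30%, which in Scenario 6 is the 0.168 dose.

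- Correct selection: (0.640 + 0.901 + 0.614 + 0.284 + 0.470)/5 = 2.909/5 = 0.58.
- Above the MTD: (0.011 + 0 + 0.040 + 0 + 0 + 0.481)/6 = 0.532/6 = 0.09.

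Most of the 0.481 in Scenario 6 is the 0.310 dose itself, selected in 0.444 of trials. In Scenarios 1 and 3, selection above the MTD falls from the published 0.026 and 0.091 to 0.011 and 0.040.

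**The case against.** The best defence is that the first two bullets state a concept and the third supplies the estimator. The third bullet is the only one that can be computed, and the 25% to 35% range, the epsilon settings and the Scenario 6 scoring all follow it. This makes it plausible that the third bullet was meant to govern. It does not remove the conflict, because an estimator that can return a dose at 33.3% does not implement a definition that excludes 30% or more.

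The percentages also depend on a reading. The first two bullets name no estimator. Using Beta(1,1) posterior means for those bullets alone, with the third bullet unchanged, moves the disagreement to about 12% to 29%. That caveat stands. It changes the size and leaves the contradiction in place.

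On Table 9-2, choosing no dose in Scenario 2 is the right decision, and the scenario is shown in full in Appendix 4. That is fair. But choosing no dose is not selecting an MTD, the table already has a row for no selection, and no note explains the scoring.

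Consequences are limited. The SRC decides by consensus on all the data, the RP2D is a composite, and Section 3.1.3 expects an RP2D before the MTD is reached. The rule matters only if toxicity reaches this zone. No sample size or stopping boundary uses 0.712. The over-MTD figure of about 0.09 is largely a scoring effect of a dose one point above 30%.

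**Conclusion.** Both points hold. Section 5.4.6.1 contradicts itself for estimates from 30% to under 35%, and nothing in the protocol or SAP resolves it. If *expected* is read as the isotonic estimate, the rules name different doses in about 7% to 22% of trials in Scenarios 1, 3, 4, 5 and 6, and never in Scenario 2. That range rests on the simulation assumptions above, which reproduce Appendix 4 with no dose's selection probability off by more than 0.011. The textual conflict rests on no assumption.

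As labelled, 0.712 is wrong. The mean over the five scenarios that have an MTD under the protocol's own scoring is 0.654, which is 0.058 lower. This is arithmetic on the published values. Confidence is high on the contradiction and on Table 9-2. The correction should be made, though SRC judgement limits the practical effect. Which rule is right is not a matter for this review.

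**What to change.** Reconcile the bullets of Section 5.4.6.1 with each other and with the acceptable range in Section 9.1.1, so that one stated rule governs. The choice belongs to the sponsor and the SRC.

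In Table 9-2, report Scenario 2 under no selection only, and give the probability of selecting the MTD as 0.654 (SD 0.193) over five scenarios.

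- If the under-35% rule is kept, the rest of Appendix 4 stands, apart from the value of 1 for selecting the MTD in Scenario 2.
- If the under-30% rule is kept, re-run Appendix 4 and Table 9-2 with that rule used both to select the dose and to define the true MTD.

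The cost is one sentence and one re-tabulated row, plus a re-run of existing simulations only in the second case.

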## 5.4.7 Recommended Dose for Further Development

The RP2D will be declared when the MTD and/or the optimal biological dose(s) is established in the Phase 1 dose escalation and/or enrichment component and/or the initial Phase 2 dose assessment part of the study. This will be a composite of safety, drug exposure, target occupancy, PK/PD association and signs of anti-tumor activity.

#### 5.4.8 Intra-patient Dose Escalation

Depending on emerging data and in the case that KY1044 as single agent or the combination with atezolizumab is well tolerated, intra-patient dose escalation of KY1044 dose may be permitted to RP2D once defined to avoid suboptimal dosing for patients treated in cohorts at lowest dose levels.

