# The overall study design is presented in Figure 3-1.

# **3.1.1 Definitions of Study Cohorts and Groups:**

# Phase 1 cohorts:

All cohorts in Phase 1 will be defined by dose level.

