7.2.3 Full Analysis Set

The full analysis set (FAS) will consist of all patients who are allocated to study drug, regardless of treatment ultimately received. Patients will be grouped according to the study drug they will be allocated to. The FAS will be the primary analysis set for efficacy endpoints.

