7.2.4 Safety Analysis Set

The safety set will consist of all patients who take at least one dose of study drug within the relevant phase. Patients will be grouped according to the study drug received at cycle 1 day 1. The safety set will be the analysis set used for safety endpoints.

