8.7.5 Dose Intensity

Absolute dose intensity (mg/week) is calculated as cumulative dose received (mg) / study treatment duration (weeks).

Relative dose intensity is calculated as the cumulative dose received (mg) / initial planned cumulative dose (mg). Initial planned cumulative dose is calculated as the starting dose (Cycle 1 Day 1 dose) multiplied by the scheduled number of administrations within the study treatment duration.

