10.0 Statistical Methods

There will be no formal statistical testing in this study. Statistical analyses will be limited to descriptive summaries.

In general, continuous variables will be summarized by number of patients, mean, standard deviation (STD), median, minimum, and maximum. The mean and median will be presented to one more and the STD to 2 more decimal places than the precision of the variable, while the minimum and maximum will be presented at the same precision. Categorical variables will be summarized by frequency counts and percentages. Percentages will be presented to one decimal place. Where relevant, estimates will be presented with 95% two-sided confidence intervals (CI).

All tables, figures and listing will be presented separately for Phase 1 and Phase 2 portion of the study.

The Phase 1 summaries will be reported by dose levels within KY1044 single agent and KY1044 with atezolizumab combination groups.

The Phase 2 of the study will be reported by indication within KY1044 single agent and KY1044 in combination with atezolizumab, split by anti-PD-(L)1 naïve and pre-treated groups, and dose levels as appropriate.

Wherever possible, patients with the same tumor type who have received the recommended dose/schedule of KY1044 as single agent or in combination with atezolizumab will be pooled for analysis, respectively.

All analyses will be performed using SAS version 9.4 or higher.

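### The SAP has no rule for data collected after a Phase 1 patient is escalated to the RP2D, so later events stay with the starting dose and switched patients can enter the RP2D pool

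*Protocol*

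**What the plan says.** Protocol 5.4.8 provides that, if treatment is well tolerated and depending on emerging data, "intra-patient dose escalation of KY1044 dose may be permitted to RP2D once defined to avoid suboptimal dosing". This covers patients who began in the lowest dose cohorts, on single agent or combination.

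The rules that decide where such a patient's data go are these:

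- **Cohorts and columns.** Protocol 3.1.1: "All cohorts in Phase 1 will be defined by dose level". SAP 10.0: "The Phase 1 summaries will be reported by dose levels within KY1044 single agent and KY1044 with atezolizumab combination groups".
- **Grouping.** Full analysis set (SAP 7.2.3): "Patients will be grouped according to the study drug they will be allocated to". Safety set (SAP 7.2.4): "Patients will be grouped according to the study drug received at cycle 1 day 1".
- **Pooling.** SAP 10.0, when feasible: "patients with the same tumor type who have received the recommended dose/schedule of KY1044 as single agent or in combination with atezolizumab will be pooled". Protocol 9.4 has nearly the same rule. Neither requires that the patient started on that dose.
- **Time origins and windows.** Baseline is the last value before first study drug (SAP 8.1). Best overall response runs from start of treatment to progression, new anti-cancer therapy, death or cut-off (8.6.1). PFS and OS run from first dose (8.6.4, 8.6.5), and DOR shares the PFS censoring rules (8.6.3). The treatment-emergent window closes at another treatment or 21 days after last dose (8.8.2). None of these mentions a dose increase.
- **Relative dose intensity.** SAP 8.7.5: "Initial planned cumulative dose is calculated as the starting dose (Cycle 1 Day 1 dose) multiplied by the scheduled number of administrations".

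The only trace of an upward change is in SAP 10.3.1, which counts patients with a dose increase and lists exposure. SAP 8.7.3 defines a reduction; an increase has no definition.

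**The concern.** The Phase 1 primary objective is to characterise safety and tolerability and to identify doses for future studies, and dose intensity is one of its primary tolerability endpoints. The dose range runs from 0.8 to 240 mg, a 300-fold span, with cohorts of about three patients. If a toxicity or response that first appears at the RP2D is reported under a very low dose, the final by-dose tables flatten the dose relationship they are meant to show.

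The pool has a different problem. To be switched, a patient must be alive and still on treatment when the RP2D is defined. Counting PFS or OS from the first low dose credits the RP2D pool with survival that was guaranteed by selection and accrued on another dose.

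**Working it through.** The plan states no figure on this point. The exact-interval routine used below reproduces all six 80% intervals in Protocol 9.2 to the rounded percent (for example 3/15: 7.6% to 39.3%, printed as 8% to 39%). The RP2D value, the switch time and the number switching are not in the documents; every such value here is an assumption.

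**1. By-dose tables.** In a three-patient starting cohort, one response arising only after escalation moves that dose from 0/3 (95% CI 0 to 70.8%) to 1/3 (0.8% to 90.6%). One late Grade 3 event moves a toxicity count in the same way. Best overall response ends at progression, so a RECIST 1.1 response can move only for a switched patient who had not progressed.

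**2. Response rate in the pool.** Start from 3/15 = 20.0% (95% CI 4.3% to 48.1%). Adding three switched patients gives 3/18 = 16.7% (3.6% to 41.4%) if none responded, or 6/18 = 33.3% (13.3% to 59.0%) if all did.

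**3. Survival in the pool.** Assume exponential survival with true 12-month OS *p*, no effect of the switch and complete follow-up to month 12. Take 15 patients who started at the RP2D and *m* patients switched at month *t*.

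- Survival to month 12 given alive at *t*: S = p^((12 − t)/12).
- Pooled 12-month OS = (15p + mS)/(15 + m).

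For p = 0.40, t = 9: S = 0.40^0.25 = 0.795. With m = 2, (6 + 1.59)/17 = 45%; with m = 5, (6 + 3.98)/20 = 50%. For t = 6: S = 0.40^0.5 = 0.632, giving 43% and 46%.

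Varying p, by the same formula:

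| True 12-month OS | t = 6, m = 2 | t = 6, m = 5 | t = 9, m = 2 | t = 9, m = 5 |
|---|---|---|---|---|
| 30% | 33% | 36% | 35% | 41% |
| 40% | 43% | 46% | 45% | 50% |
| 50% | 52% | 55% | 54% | 59% |

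The upward shift is about 2 to 11 percentage points, with no true difference between patients.

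**4. Relative dose intensity (SAP 8.7.5).** Cumulative dose divided by (Cycle 1 Day 1 dose × scheduled administrations). Eight infusions at 2.4 mg then eight at an assumed 24 mg: (19.2 + 192)/(16 × 2.4) = 211.2/38.4 = 5.5, or 550%. Across starts of 0.8 to 8 mg, an assumed RP2D of 24 to 240 mg, and switches after 4 of 8, 8 of 12 or 12 of 16 doses, the ratio runs from 1.5 to 150.5.

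**5. Choice of a new denominator.** Suppose the last four infusions in that example are cut to 8 mg for toxicity. The dose received is 19.2 + 96 + 32 = 147.2 mg. If planned dose followed whatever was assigned each cycle, the ratio would be 147.2/147.2 = 100% and the intolerance would vanish. Keeping the planned dose at the escalated level gives 147.2/211.2 = 70%.

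**The case against.** Much can be said on the other side, and most of it limits the point without removing it.

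- **Timing.** A reader might infer that post-switch data contaminate the RP2D choice or the MTD. The documents do not support that. Escalation is allowed only once the RP2D is defined, so those data cannot have fed the declaration that permitted the switch. DLTs are counted in the first 21 days, and Cycle 1 safety and PK are at the starting dose.
- **Progression.** A patient with RECIST progression before the switch cannot gain a RECIST 1.1 response, and the PFS event is already fixed. This stands.
- **Wording.** SAP 7.2.3 and 7.2.4 group by study drug, not dose. The starting-dose column follows from reading them with the dose-defined cohorts and by-dose reporting; no sentence states it. This stands, and is itself a reason to write the rule down.
- **Separate phases.** SAP 10.0 presents all output separately for Phase 1 and Phase 2. That makes it hard to add Phase 1 switched patients to a Phase 2 cohort, but a Phase 1 RP2D pool stays exposed.
- **Size.** Escalation is optional, and pooling is only where possible and within tumor type. Five switched patients of one tumor type and one treatment group is an extreme case, and the number could be zero.
- **Disclosure.** Increases are counted, exposure is listed and absolute dose intensity is reported. A reader could identify switched patients, but the tables would still attribute their outcomes as described.

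**Conclusion.** The point holds in a bounded form. Followed as written, the plan leaves post-Cycle-1 adverse events, and responses in switched patients without earlier RECIST progression, in the starting-dose column. It lets the same patients into an RP2D pool with immortal time in PFS and OS, mainly within Phase 1, and it pushes relative dose intensity above 100%. It would go too far to conclude that no by-dose result reflects the dose given: the data of patients who never switch, and everything in Cycle 1, are sound.

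The 43% to 50% survival figures and the 550% are illustrations under assumed inputs, not estimates for this trial. The direction of the immortal-time effect does not depend on those inputs; its size depends on how many patients switch and when. All analyses are descriptive, so no error rate is at stake. The change should be made, because the affected tables serve the Phase 1 primary objective and the repair is cheap. Nothing here bears on whether escalation should be permitted or to what dose.

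**What to change.** Amend SAP 7.2, 8.6, 8.7.5, 8.8.2 and 10.0:

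1. **By-dose tables.** Keep the as-allocated tables. Derive the date of the first infusion above the assigned dose, and show responses and adverse events with onset after it in a separate column labelled as after intra-patient escalation. State that the SAP 8.1 baseline is retained. A PFS/DOR version censored at escalation may be added only as a supplement: patients who switch are selected for still being on treatment and tolerating it, so that censoring may be informative, and the SAP should say so.
2. **RP2D pool.** Define it as patients whose Cycle 1 Day 1 dose was the RP2D, as the working definition of the Protocol 9.4 rule.
3. **Relative dose intensity.** Use the Cycle 1 Day 1 dose as planned dose up to the escalation and the escalated dose level thereafter. Do not lower the planned dose for toxicity-driven reductions.

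The exposure CRF pages already record the actual dose at each administration, so no new data are needed. The cost is a little extra programming and one extra column.
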